9.2. Setting

[figure not shown]
This study will be conducted using data from four Nordic countries: Denmark, Finland, Norway, and Sweden.⁸ All live births and stillbirths are recorded in birth registries (in all countries except Sweden from gestational week 22 from July 2008 onwards; in Sweden, from gestational week 28 from July 2008 onwards). During the study period, there were approximately 580,000 – 730,000 live births in each of Denmark, Finland, and Norway, and 1,100,000 in Sweden.⁹ The start of the study period in each country was selected to ensure availability of gabapentin and the comparators on the market and availability of data on outpatient dispensings for at least 12 months before the end of the earliest identified pregnancy. For example, pregnancy ending at term with a live birth on 1 January 2005 in Denmark will have prescription history from 1 January 2004, thus covering the 9 months of gestation and 3 months preconception.

Population-based healthcare registries in Nordic countries are an optimal setting for examining safety of medicines in pregnancy. Their most important strengths are capture of all births and, clinically relevant birth and postnatal outcomes for this study; last menstrual period (LMP), depending on country is either directly recorded in the birth registry or estimated from gestational age; routine capture of dispensings of prescription medications to pregnant women; extensive information about maternal and offspring demographic information; and exact linkage between the maternal and the offspring record.

Study population

The study population will consist of all births identified in the respective registries from 1 January 2005 to 31 December 2015 in Denmark, Finland, and Norway and all births identified from 1 July 2006 to 31 December 2016 in Sweden, [Figure 1](#) .

Figure 1. Study population flow diagram

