As all birth outcomes will have occurred as of the date of delivery, prevalence will be used as a measure of outcome occurrence.¹⁰ To allow for delayed reporting/diagnosis, all congenital malformations diagnosis recorded within one year of age will be included, according to the standard procedure used by the European Network of Congenital Anomaly Registers (EUROCAT)¹¹ through the end of 2016 in Denmark, Finland and Norway and through the end of 2017 in Sweden. In addition, available information on pregnancies ending in 2nd trimester therapeutic induced abortions will be identified in Denmark, Finland and Norway. Information on pregnancies ending in 2nd trimester therapeutic induced abortions is not available from Sweden for the specific study period. It will be especially important to identify pregnancy terminations due to malformations of the nervous system, as nearly half of the pregnancies affected by nervous system malformations may be terminated.¹²

Major congenital malformations and stillbirth prevalence will be described and compared using live and stillbirths as the denominator. For the birth outcomes other than major congenital malformations or stillbirth, prevalences at birth will be described and compared using live births as the denominator.

For the postnatal neurodevelopmental outcomes, livebirths of all gabapentin-exposed and the comparator pregnancies will be followed from the date of birth until the earliest record of a given outcome of interest, emigration (except Sweden and Norway, where emigration data are unavailable), death, or end of study (31 December 2016 in Denmark, Finland, and Norway; 31 December 2017 in Sweden); for this analysis, children in Norway born before 2008 will be excluded as the Patient Registry of Norway was launched in 2008. Thus, for the neurodevelopmental postnatal outcomes, livebirths will be followed up to a minimum of 1 year and a maximum of 8 years in Norway, 10 years postnatally in Denmark, and Finland, and up to a maximum 11.5 years postnatally in Sweden (Figure 2).

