9.2.1. Inclusion criteria

All births from 1 January 2005 through 31 December 2015 (both dates inclusive) in Denmark, Finland, and Norway and all births identified from 1 July 2006 through 31 December 2016 (both dates inclusive) in Sweden.

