9.3.3. Covariates and other population characteristics

Characteristics of the study population that are to be described will include calendar year of delivery, maternal age at conception, parity (number of live and still births prior to the on-study pregnancy); indication for AED use, marital/cohabiting status; pregravid body mass index (BMI) as recorded at the first antenatal visit or via a hospital diagnosis of obesity; smoking during pregnancy as recorded at the first antenatal visit; single or multiple gestation; Caesarean delivery; and child's sex. Caesarean delivery and child's sex will be reported but will not be used for adjustment. Indication for gabapentin (and other AEDs) use in 12-months pre-LMP (epilepsy, neuropathic pain, 'other' indications) will be reported

descriptively but will not be used for adjustment as administrative data available for this study have low sensitivity in identifying relevant indications for all pregnancies.

[figure not shown]
The covariates to be included in the propensity-score model are:

- calendar year of delivery;
- maternal age in years at conception;
- marital/cohabiting status;
- smoking during pregnancy;
- obesity (BMI \geq 30 kg/m²) or a hospital diagnosis of obesity;
- single or multiple gestation;
- hospital-recorded morbidity based on inpatient and outpatient specialist care or proxy medication use in 12 months pre-LMP: migraine or other headache syndromes, other neurologic disorders, depression, bipolar disorder, alcohol abuse or dependence, drug abuse or dependence, hypertension, haematological diseases, diabetes, asthma, liver diseases, renal impairment, rheumatic diseases, obesity, disorders of female pelvic organs/genital tract, thyroid disorders, infections (infections will be assessed in 90 days pre-LMP). In Finland, in addition to the hospital diagnoses, diagnoses from primary care are also available and will be used;
- indicators of maternal health care utilisation in the 12 months pre-LMP (number of inpatient and specialised outpatient encounters);

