Study variable/role	Type of data	Data source(s)	Coding system(s) used
	Maternal morbidity (including indication for gabapentin) Markers of health care utilisation	Danish National Patient Registry, ³² Finnish Care Register for Health Care Finnish Register of Primary Health Care visits Norwegian Patient Registry ³⁷ Swedish National Patient Register ⁴³ Danish National Prescription Registry ³⁴ FinnishDatabase Finnish Prescription Register ³⁵ Norwegian Prescription Database ³⁵ Swedish Prescribed Drug Register ³⁵	ICD-10 for diagnoses, ATC for medication proxies
	Maternal medications	Danish National Prescription Registry ³⁴ Finnish Prescription Register ³⁵ Norwegian Prescription Database ³⁵ Swedish Prescribed Drug Register ³⁵	ATC
Loss to follow-up	Death, emigration [†]	Danish Civil Danish Civil Registration System ³⁰ Finnish Causes of Death Register Finnish Population Register Centre National Registry of Norway Swedish Cause of Death Register ⁴⁴ Swedish Total Population Register	A specific variable in each registry

*Data for the Medical Birth Register, the Register on Induced Abortions, the Malformation Register and the Prescription Register (3 months before last menstrual period) can be obtained from the Finnish Drugs and Pregnancy Project (DPP) database.

[†]Emigration data not available in the Norwegian dataset

[‡]Data available from 2008 onwards in Norway

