9.7.3.1. Computation of propensity scores

To account for confounding by all measured covariates, adjusted analysis will be conducted using propensity score (PS) stratification, following the approach by Paterno et al.⁵⁰ For each pregnancy, a PS will be computed, using logistic regression, as the probability being exposed

to gabapentin vs. given comparator conditional on the measured covariates listed in [Section 9.3.3](#) and [Annex 3](#).⁵¹

PS will be estimated for each birth using a generic-outcome model, meaning that all prespecified covariates will be included in the PS-estimating model, regardless of the association with the outcome. Wyss et al showed, in a simulation study, that such a model performs well when multiple outcomes are being examined;⁵² furthermore, it is reasonable to assume in this study that all confounders distort the association in the same direction for all outcomes. In case of model non-convergence, covariates with the smallest cell counts (corresponding to the lowest prevalence of covariates) will be removed one-by-one until convergence is achieved. Categories of variables with small cell counts may be collapsed if applicable by an analyst in each country.

A separate PS will be estimated for each study population and comparison. To summarise, the following sets of propensity scores will be estimated:

1. First-trimester gabapentin (monotherapy or polytherapy) vs. first-trimester unexposed to AEDs
2. First-trimester gabapentin (monotherapy or polytherapy) vs. first-trimester pregabalin (monotherapy or polytherapy)
3. First-trimester gabapentin (monotherapy or polytherapy) vs. first-trimester lamotrigine (monotherapy or polytherapy)
4. First-trimester gabapentin (monotherapy or polytherapy) vs. first-trimester pregabalin or lamotrigine (monotherapy or polytherapy)
5. First trimester gabapentin (monotherapy only) vs. first-trimester unexposed to AEDs
6. First trimester gabapentin (monotherapy only) vs. first-trimester pregabalin (monotherapy only)
7. First trimester gabapentin (monotherapy only) vs. first-trimester lamotrigine (monotherapy only)
8. First-trimester gabapentin (monotherapy only) vs. first-trimester pregabalin or lamotrigine (monotherapy only)
9. Any-trimester gabapentin (monotherapy or polytherapy) vs. any-trimester unexposed to AEDs
10. Any-trimester gabapentin (monotherapy or polytherapy) vs. any-trimester pregabalin (monotherapy or polytherapy)

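### The propensity score needs 12 months of pre-LMP hospital history, but Norway's only named hospital source starts in 2008 while Norwegian births from 2005 stay in the primary analyses

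*Protocol*

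**What the plan says.** Section 9.3.3 lists the covariates of the propensity-score model. Two depend on hospital data before pregnancy: "hospital-recorded morbidity based on inpatient and outpatient specialist care or proxy medication use in 12 months pre-LMP", and "indicators of maternal health care utilisation in the 12 months pre-LMP (number of inpatient and specialised outpatient encounters"). Section 9.7.3.1 adds that "all prespecified covariates will be included in the PS-estimating model, regardless of the association with the outcome".

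Section 9.2.1 includes "All births from 1 January 2005 through 31 December 2015 (both dates inclusive) in Denmark, Finland, and Norway". Table 1 repeats these dates for all primary outcomes.

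For maternal morbidity and health-care utilisation in Norway, Table 2 (Section 9.4) names the Norwegian Patient Registry and the Norwegian Prescription Database. Only the first holds hospital contacts. Section 9.2 recognises its late start, but only for the children's neurodevelopmental outcomes: "for this analysis, children in Norway born before 2008 will be excluded as the Patient Registry of Norway was launched in 2008". Footnotes to Tables 1 and 2 also give 2008.

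For Finland, a footnote to Table 2 says that "the Prescription Register (3 months before last menstrual period) can be obtained from the Finnish Drugs and Pregnancy Project (DPP) database".

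**The concern.** The birth dates, the covariate list, the look-back window and the data source are all fixed in the protocol, and for Norway they cannot all hold. A birth in 2006 has no record in a registry that opened in 2008. The 2008 start was acted on for the child outcomes and not for the mothers' covariates.

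These covariates carry weight here. Section 9.3.3 leaves indication out of the adjustment because it is poorly recorded, and Section 9.9 concedes that the unexposed population is likely to be healthier. Morbidity and utilisation are therefore a large part of what remains to control confounding, above all against births unexposed to AEDs. Section 9.7.7 also justifies fixed-effects pooling partly by covariates that are well defined and common to all countries. A look-back that is absent in one country for part of the period weakens that premise.

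Section 9.9 discusses the missing Norwegian emigration data but not this gap, and the ENCePP checklist (item 10.5) marks methods for missing data as not applicable.

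**Working it through.** **Inputs.** Norwegian birth window: 1 January 2005 to 31 December 2015, 4,017 days (Section 9.2.1). Registry start: 2008 (Section 9.2), taken as 1 January. Gestation: 280 days, the value that Section 9.3.1 uses to impute LMP. Norwegian births 2005-2015: 657,451 (Table 3, Section 9.9). Norwegian gabapentin exposures: 344 in the first trimester and 467 at any time (Table 3). Section 9.9 sets the 467 against the 657,451 births.

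**The plan's own figure.** The protocol gives no share of births without look-back. Its one related figure is the Danish dispensing example in Section 9.2: for a term birth on 1 January 2005, history from 1 January 2004 is described as "thus covering the 9 months of gestation and 3 months preconception". Check: 1 January 2005 minus 280 days is an LMP of 27 March 2004, which leaves 86 days, or 2.8 months. The date method reproduces it.

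**Norwegian births without hospital look-back.** Share = days from 1 January 2005 to the cut-off / 4,017, with births spread evenly.

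- No pre-LMP history (LMP before 1 January 2008): births before 7 October 2008. (1,095 + 280) / 4,017 = 1,375 / 4,017 = 34.2%, about 225,000 births.
- Less than the full 12 months (LMP before 1 January 2009): births before 8 October 2009. (1,461 + 280) / 4,017 = 1,741 / 4,017 = 43.3%, about 285,000 births.

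These are two definitions, not the ends of an uncertainty range.

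| Assumption varied | No history | Under 12 months |
|---|---|---|
| Gestation 259 to 287 days | 33.7-34.4% | 42.8-43.5% |
| Linear trend in births of ±20% over the period | 32-36% | 41-46% |

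**Exposed pregnancies.** With even use over time, the two shares give 118 and 149 of the 344 first-trimester exposures, and 160 and 202 of the 467 at any time. If use rose linearly r-fold over the window (an assumption), a calendar share f becomes [f + (r-1)f²/2] / [1 + (r-1)/2]:

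- r = 2: 26.7% and 35.2%
- r = 4: 20.7% and 28.6%

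**Weight in the pooled analysis.** Table 3 totals 1,592 first-trimester exposures. 118 / 1,592 = 7.4% and 149 / 1,592 = 9.4%, again with even use.

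**The case against.** Several stronger readings are tempting, and the documents do not support them.

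- *The early Norwegian births are not adjusted for comorbidity at all.* The covariate allows drug proxies as an alternative to hospital diagnoses, and Table 2 lists the Norwegian Prescription Database for maternal morbidity with no 2008 limit. Section 9.3.3 also enters 13 medication classes measured in the exposure window. What is lost is the contact counts and the conditions without a drug proxy.
- *Missing history will be coded as absent.* That is a plausible default, but no section says so, and a statistical analysis plan could set the coding. It could not create records from before 2008.
- *The balance check must pass because the covariates are zero in both arms.* Section 9.7.3.1 assesses standardised mean differences in each country's whole dataset, where later births supply non-zero values. The valid criticism is narrower: the check does not look at the early births separately.
- *Finland cannot supply 12 months of dispensings.* The footnote says that data can be obtained from the project database, and Table 2 also lists the Finnish Prescription Register directly. Finnish hospital and primary-care diagnoses carry no such limit. This is an ambiguity to resolve.
- *Denmark and Sweden have the same defect.* Section 9.2 sets only a minimum dispensing history. If dispensings began on 1 January 2004, 280 / 4,017 = 7.0% of an 11-year window would lack 12 months, for drug proxies only. The Swedish start date would have to be inferred. This is not part of the point.

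It is also fair that calendar year is in the score, that scores are fitted within country and may differ between countries, and that heterogeneity is examined. None of this supplies the missing contact counts. The case against is right that the pooled weight is modest and that no bias in any ratio has been shown.

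**Conclusion.** The protocol contradicts itself for Norway. It requires 12 months of pre-LMP hospital data for births that its only named hospital source cannot cover. About 34% of Norwegian births have none of that history and about 43% lack some of it, given even births, a 280-day gestation and a 1 January 2008 start. Among exposed births the shares are lower if use grew, about 21-35% across both definitions under the assumed 2- to 4-fold rise.

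Followed as written, the plan would report adjusted ratios in which births without that history are not adjusted for utilisation or for conditions lacking a drug proxy, and the reader would not be told. The direction and size of any resulting bias cannot be derived from the document.

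**What to change.** In Sections 9.3.3 and 9.7.3.1, for Norway:

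1. Treat look-back that cannot be observed as not available, never as absence of the condition or zero contacts.
2. Estimate the propensity scores separately for LMP before and from 1 January 2009. In the earlier period use only covariates that can be observed: birth-registry variables, drug proxies and the medication classes. Combine the two periods as strata.
3. As a sensitivity analysis, report Norwegian and pooled results with Norway restricted to LMP from 1 January 2009.
4. List the gap in Section 9.9.

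In Section 9.4, state whether Finnish prescriptions come from the project extract (3 months before LMP) or from a direct 12-month extract.

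Cost: the split doubles the Norwegian propensity-score runs. Section 9.7.3.1 lists 16 contrasts, and Section 9.7.6 adds separate sets for its sensitivity analysis. Adjustment stays weaker in the early stratum. Early counts will be small: at the planning prevalence of 3%, 118 to 149 exposed births give 0.03 × 118 = 3.5 to 0.03 × 149 = 4.5 expected malformations. That is under the limit of 5 events in Section 9.7, so the early stratum may not be reportable on its own. The later-period and combined Norwegian results are therefore the ones to plan on presenting.

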9.3.2.2. Secondary Outcomes (Postnatal neurodevelopmental outcomes)

Postnatal neurodevelopmental outcomes (ICD-10 (International Classification of Diseases, Tenth Revision) codes):

- Attention-deficit hyperactivity disorders (F90);
- Pervasive developmental disorders (autism spectrum disorders) (F84);

- Learning disorders (Specific developmental disorders of speech and language (F80), and Specific developmental disorders of scholastic skills (F81)) and Intellectual disabilities (mental retardation) (F70-F79).

Follow-up for the postnatal neurodevelopmental outcomes, when available, will be a minimum of 1 year postnatally and for the maximum period available in the dataset for each birth. However, for a variety of reasons (e.g. emigration, death), follow-up could be infeasible in individual cases. It should be noted that not all livebirths will have available follow-up information into the school age, and as postnatal neurodevelopmental disorders are diagnosed primarily at school age, the number of events in gabapentin exposed (and other comparator groups) pregnancies in the study period may not be sufficient to yield stable estimates of association.¹⁶

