- for the outcome congenital malformations: maternal medication use each as a dichotomous variable, defined by at least one dispensing during the first trimester (AEDs, antidepressants, hypnotics, antipsychotics, analgesics, antihypertensives, non-steroidal anti-inflammatory drugs, drugs for peptic ulcer/gastroesophageal reflux, folic acid, drugs for in-vitro fertilization, thyroid hormones, systemic corticosteroids, and anti-infectives for systemic use);
- for the outcomes other than congenital malformations: maternal medication use each as a dichotomous variable, defined by at least one dispensing during any trimester (AEDs, antidepressants, hypnotics, antipsychotics, analgesics, antihypertensives, non-steroidal anti-inflammatory drugs, drugs for peptic ulcer/gastroesophageal reflux, folic acid, drugs for in-vitro fertilization, thyroid hormones, systemic corticosteroids, and anti-infectives for systemic use).

[figure not shown]
Full list of the study variables and their operational definitions are provided in [Annex 3](#).

Figure 2. Examples of follow up period for neurodevelopmental outcomes during the study period

[figure not shown]
1.

2.

3.

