9.7. Data analysis

For all data analyses, the birth (not the patient/mother) will be the unit of analysis. Given that a woman could have more than one birth during the study period, data analyses will account for correlated observations using GEE (generalized estimating equation) or robust variance estimates. All steps of the country-specific data analyses will be conducted separately in each participating country according to the description below. Each country will generate a set of identical analytic tables. Registry data will not be provided for very low numbers (less than 5 events) due to data security and data confidentiality rules.

After conducting the country-specific data analyses, country-specific datasets containing crude and adjusted estimates of association will be transferred to Aarhus University Hospital, Denmark, for meta-analyses.

Given that gabapentin has several indications and that administrative data available for this study have low sensitivity in identifying relevant indications for all pregnancies, in this study pregnancies exposed to gabapentin will be compared with pregnancies exposed to medications with similar sets of indications. Because confounding by indication or severity

of indication may persist even against an active comparator,⁷ the amount of confounding may be inferred indirectly by examining whether estimates of association differ depending on the comparator. Here, pregabalin and lamotrigine, which are both indicated for epilepsy, have been identified as suitable active comparators.

In a 2019 publication from Sweden, all individuals aged 15 years or older and being dispensed at least 2 prescriptions of gabapentin in the period 2006-2013 were identified (N=85,360).⁴⁹ The indication of use (i.e. health status before start of treatment) was 6.4% epilepsy, 20% psychiatric disorders, and 52.1% musculoskeletal disorders. In the same publication, the indication of use for pregabalin (n=120,664) was 5.4% epilepsy, 40.9% psychiatric disorders, and 46.2% musculoskeletal disorders. Published data on the most common gabapentin indication in pregnant women are unavailable at this time.

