9.7.5. Secondary analyses

The secondary analyses will be conducted among live-born children. In these analyses any trimester gabapentin exposure will be considered versus each of the comparators as above. The monotherapy subset will be examined, sample size permitting.

Incidence rates (number of events/person-time contributed by live-births) of the postnatal neurodevelopmental outcomes will be reported according to any prenatal exposure to gabapentin and the predefined comparators. All incidence rates will be reported for any gabapentin therapy and the subset with gabapentin monotherapy.

For the postnatal neurodevelopmental outcomes, exposure will be defined at any time during pregnancy. Crude and PS-adjusted hazard ratios will be estimated using Cox's proportional-hazards regression. In the event that too few postnatal outcomes are observed to estimate association, the number of cases and crude rates will be reported to the extent allowed by the data protection regulation.

To summarise, the following comparative analyses will be performed for all outcomes:

- Any-trimester gabapentin (monotherapy or polytherapy) vs. any-trimester unexposed to AEDs
- Any-trimester gabapentin (monotherapy or polytherapy) vs. any-trimester pregabalin (monotherapy or polytherapy)
- Any-trimester gabapentin (monotherapy or polytherapy) vs. any-trimester lamotrigine (monotherapy or polytherapy)
- Any-trimester gabapentin (monotherapy or polytherapy) vs. any-trimester pregabalin or lamotrigine (monotherapy or polytherapy)

Sample size permitting:

- Any-trimester gabapentin (monotherapy only) vs. unexposed to AEDs
- Any-trimester gabapentin (monotherapy only) vs. any-trimester pregabalin (monotherapy only)
- Any-trimester gabapentin (monotherapy only) vs. any-trimester lamotrigine (monotherapy only)
- Any-trimester gabapentin (monotherapy only) vs. any-trimester pregabalin or lamotrigine (monotherapy only)

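### The propensity score behind the child ADHD, autism and learning or intellectual disability hazard ratios has no maternal neurodevelopmental covariate, so part of the familial risk may remain

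*Protocol*

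**What the plan says.** Section 9.3.3 introduces its list with "The covariates to be included in the propensity-score model are", with no wording that marks the items as examples. The neurologic and psychiatric diagnoses are among "migraine or other headache syndromes, other neurologic disorders, depression, bipolar disorder, alcohol abuse or dependence, drug abuse or dependence, hypertension"; the rest of the morbidity list is somatic. For outcomes other than malformations, maternal medication in any trimester is added, beginning "AEDs, antidepressants, hypnotics, antipsychotics, analgesics, antihypertensives, non-steroidal anti-inflammatory drugs". No ADHD drug class follows. The list also has smoking and counts of inpatient and specialist encounters.

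Section 9.7.3.1 uses one covariate set for all outcomes: "PS will be estimated for each birth using a generic-outcome model, meaning that all prespecified covariates will be included in the PS-estimating model". It conditions the score on section 9.3.3 and Annex 3. The codes in Annex 3 are not in the text at hand.

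The secondary outcomes in section 9.3.2.2 include "Attention-deficit hyperactivity disorders (F90"), pervasive developmental disorders (F84), and learning disorders (F80, F81) together with intellectual disability (F70-F79). Section 9.7.5 analyses them thus: "Crude and PS-adjusted hazard ratios will be estimated using Cox's proportional-hazards regression".

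Section 9.4 states that each child can be linked exactly to the mother's dispensings and diagnoses before and during pregnancy. Table 2 draws maternal morbidity from national patient and prescription registers.

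**The concern.** The outcomes are disorders with a familial component, and a mother's own diagnosis of the same kind is an obvious candidate confounder. It predicts the child's outcome, and it may be more common among women who are dispensed gabapentin. A list built to serve birth outcomes and neurodevelopmental outcomes alike can easily miss a confounder that matters for only one of the two groups, and this one does. The only outcome-specific tailoring in section 9.3.3 is the time window for medication.

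The planned safeguards would not expose the gap. Balance is judged on the covariates in the model (section 9.7.3.1), and maternal neurodevelopmental diagnosis is neither a covariate nor one of the characteristics to be described. Section 9.9 discusses short follow-up and detection bias for these outcomes but not familial risk. Low sensitivity is given as the reason for not adjusting for indication; no reason is given for this omission.

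At stake is how an adjusted hazard ratio moderately above 1 against unexposed births would be read. Pooling four countries narrows the interval but does not remove a bias that they share.

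**Working it through.** **1. The protocol's own precision figures.** Inputs: 1,743 pregnancies exposed at any time and 3,298,823 in total (section 9.5), true ratio 1, z-values 1.960 and 0.842.

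SE = √[(1−p)/(n₁p) + (1−p)/(n₀p)], upper limit = exp(2.802 × SE), with n₁ = 1,743 and n₀ = 3,298,823 − 1,743 = 3,297,080.

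- ASD row, p = 0.6%: SE = 0.308, upper limit 2.373. Table 4 states 2.373.
- ADHD row, p = 1%: SE = 0.238, upper limit 1.950. Table 4 states 1.950.

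Both reproduce. They assume no residual confounding.

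**2. Size of the omission against unexposed births.** The documents give none of the three inputs, so all are assumptions: p₁ = share of exposed births with an affected mother (2-8%), p₀ = the same in unexposed births (0.5-1%), R = risk ratio for the child's outcome given an affected mother (2-4).

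Bias factor B = [1 + p₁(R−1)] / [1 + p₀(R−1)]

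- p₁ = 2%, p₀ = 1%, R = 2: 1.02/1.01 = 1.010
- p₁ = 5%, p₀ = 0.5%, R = 4: 1.15/1.015 = 1.133
- p₁ = 8%, p₀ = 0.5%, R = 4: 1.24/1.015 = 1.222

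The formula takes no account of the covariates already in the score, so B overstates what remains to the extent that they act as proxies. If p₁ = p₀, B = 1.

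**3. Consequence with no drug effect.** The chance that the lower 95% limit exceeds 1 is 1 − Φ(1.960 − ln B/SE). It is 2.5% when B = 1.

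| B | ln B | ASD (SE 0.308) | ADHD (SE 0.238) |
|---|---|---|---|
| 1.010 | 0.010 | 2.7% | 2.8% |
| 1.133 | 0.125 | 6.0% | 7.5% |
| 1.222 | 0.200 | 9.5% | 13.1% |

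The chance of excluding the Table 4 limit, planned at 80%, becomes 79%, 67% and 58% for ASD and 79%, 62% and 50% for ADHD.

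**4. How much adjustment would remove.** Registers miss some affected mothers. With sensitivity s and perfect specificity (both assumed), the share of affected mothers among those without a record is q = p(1−s)/(1−ps), and q₁ and q₀ replace p₁ and p₀ in the formula for B. For the largest case above (B = 1.222):

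- s = 30%: q₁ = 5.74%, q₀ = 0.35%, remaining B = 1.16
- s = 50%: q₁ = 4.17%, q₀ = 0.25%, remaining B = 1.12
- s = 80%: q₁ = 1.71%, q₀ = 0.10%, remaining B = 1.05

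The change reduces the bias but does not remove it.

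**The case against.** **Existing covariates already carry part of this risk.** Depression, bipolar disorder, substance abuse, antidepressants, antipsychotics, hypnotics, smoking and encounter counts are plausible proxies. This stands: only part of the familial risk may remain. Paternal risk lies outside the list before and after any change.

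**Annex 3 may hold the codes.** The score is conditioned on it and its content cannot be seen. Section 9.3.3 reads as a definitive list, so the omission is likely, but it needs confirmation.

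**The size is assumed throughout.** True. The low end is negligible, and the protocol already calls these outcomes secondary and warns of unstable estimates. Imprecision, however, does not excuse a bias that linked data could reduce.

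**Register look-back is uneven.** Also true, and it limits the benefit (see the fix).

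Two stronger readings are tempting but unsupported:

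- A reader might infer that the omission contradicts the statement "it is reasonable to assume in this study that all confounders distort the association in the same direction for all outcomes". That assumption concerns consistency across outcomes. A bias that differed between the unexposed and pregabalin comparisons would be a difference across comparators, on which the statement is silent. Section 9.7 in fact proposes to infer confounding from differences between comparators.
- A reader might infer from the cited Swedish data that the bias against pregabalin runs downward and could hide a signal. Those data give 20% psychiatric disorders for gabapentin users and "5.4% epilepsy, 40.9% psychiatric disorders, and 46.2% musculoskeletal disorders" for pregabalin users. They cover everyone aged 15 or older with at least two gabapentin dispensings and the corresponding pregabalin group, not pregnant women. They concern psychiatric disorders in general, and they include no unexposed group and no lamotrigine group. They do not establish a direction for maternal neurodevelopmental diagnoses.

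**Conclusion.** The point holds as a moderate gap in confounding control for the secondary outcomes. On the text available, the score used for child ADHD, autism and learning or intellectual disability contains no maternal diagnosis of the same kind and no ADHD medication, and section 9.9 does not acknowledge the resulting bias. Against unexposed births the inflation is a factor of about 1.01 to 1.22 under the stated assumptions, before allowing for the proxies. Against pregabalin, lamotrigine or the two combined, neither size nor direction can be derived. The conclusion depends on Annex 3 not already supplying the codes. It does not touch the malformation or other birth outcomes, and it is not an error in the study-size calculation: the two Table 4 rows checked here reproduce exactly.

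**What to change.** First confirm whether Annex 3 already contains these variables. If not, add the following to the any-trimester propensity scores used for the postnatal outcomes:

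- maternal ADHD (F90 or a dispensing of ADHD medication);
- maternal pervasive developmental disorder (F84);
- maternal learning disorders (F80-F81);
- maternal intellectual disability (F70-F79).

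Define each as recorded at any time before LMP, as far as each register allows; the 12-month window used for other morbidity suits lifelong conditions poorly. Where counts are sparse, collapse them into one yes/no variable; section 9.7.3.1 already lets analysts collapse sparse categories. State in section 9.9 that residual familial confounding, including paternal risk, is expected.

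The cost is a few extra codes, mostly on registers already listed for maternal morbidity. The downside is incomplete and uneven capture. Norwegian patient data start in 2008, Table 2 lists the Danish psychiatric registers only for child outcomes, and dispensing history before the earliest pregnancies is short. If maternal use of the Danish psychiatric registers needs a further data permission, that adds to the cost. Only part of the bias would be removed, and the report should say so.
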